6. SUBJECT SELECTION AND WITHDRAWAL

6.1 Inclusion Criteria

1. Histologically confirmed diagnosis of cSCC.
2. Unresectable or metastatic cSCC.
3. History of solid-organ transplant requiring immunosuppression
4. Allowable prior therapies:
 - a. A maximum of 4 prior therapies for metastatic disease are allowed.
5. Male or female subjects, age 18 years or older.
6. ECOG performance status ≤ 2 (Appendix A)
7. Life expectancy of ≥ 3 months.
8. Laboratory parameters within the following Protocol-defined range. All screening laboratory tests should be performed within 28 days of treatment initiation and must be independent of hematopoietic growth factor support.
 - Absolute neutrophil count $\geq 1.5 \times 10^9/L$.
 - Platelets $\geq 100 \times 10^9/L$.
 - Hemoglobin $\geq 9 \text{ g/dL}$ (transfusion is acceptable to meet this criteria)
 - Serum creatinine $\leq 1.5 \times$ institutional upper limit of normal (ULN) OR calculated creatinine clearance $\geq 50 \text{ mL/min}$ for subjects with creatinine levels $> 1.5 \times$ institutional ULN.
 - Aspartate aminotransferase, alanine aminotransferase, alkaline phosphatase $\leq 2.5 \times$ ULN, or $\leq 5 \times$ ULN in subjects with liver metastases.
 - Total bilirubin $\leq 1.5 \times$ ULN
 - **Note:** patients with hyperbilirubinemia clinically consistent with an inherited

disorder of bilirubin metabolism (eg, Gilbert syndrome) will be eligible at the discretion of the principal investigator.

- International normalized ratio (INR) or prothrombin time (PT) $< 1.5 \times$ ULN unless subject is receiving anticoagulation therapy as long as PT or INR is within therapeutic range of intended use of anticoagulant.
- Activated partial thromboplastin time (aPTT) $< 1.5 \times$ ULN unless subject is receiving anticoagulant therapy, as long as PTT is within therapeutic range of intended use of anticoagulants.

9. Presence of baseline measureable disease by RECIST v1.1 for solid tumors, defined as at least one lesion that can be accurately measured in at least one dimension (longest diameter to be recorded for non-nodal lesions and short axis for nodal lesions) as ≥ 20 mm with conventional techniques or as ≥ 10 mm with spiral CT scan, MRI, or calipers by clinical exam. (See Section 15.4 for the evaluation of measurable disease).
10. The effects of ruxolitinib on the developing human fetus are unknown, and thus female subjects of childbearing potential (defined as women who have not undergone surgical sterilization with a hysterectomy and/or bilateral oophorectomy, and are not postmenopausal (defined as ≥ 12 months of amenorrhea)) must have a negative pregnancy test at screening and must agree to use adequate contraception (complete abstinence, or two methods of birth control (Appendix B)) prior to study entry and until at least 4 months after the last dose of study treatment. Should a woman become pregnant or suspect she is pregnant while she or her partner is participating in this study, she should inform her treating physician immediately.
11. Fertile men must also agree to use adequate contraception (2 barrier methods or abstinence) during the study and for up to 4 months after the last dose of study drug.
12. Subjects must agree to pre- and on-treatment tumor biopsies. Subjects in whom biopsy is technically not feasible or in whom would result in unacceptable risk, in the opinion of the investigator, may be exempted from the biopsy requirement with discussion with the principal investigator. Use of outside archived tumor tissue for a baseline biopsy is not permitted.
13. Willingness and ability to provide written informed consent prior to any study-related procedures and to comply with all study requirements.

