15.3 Disease Parameters

Measurable disease: Measurable lesions are defined as those that can be accurately measured in at least one dimension (longest diameter to be recorded for non-nodal lesions and short axis for nodal lesions) as ≥ 20 mm by chest x-ray, as ≥ 10 mm with CT scan or MRI, or ≥ 10 mm with

calipers by clinical exam. All tumor measurements must be recorded in millimeters (or decimal fractions of centimeters).

Note: Tumor lesions that are situated in a previously irradiated area might or might not be considered measurable. If the investigator thinks it appropriate to include them, the conditions under which such lesions should be considered must be defined in the protocol.

Malignant lymph nodes: To be considered pathologically enlarged and measurable, a lymph node must be ≥ 15 mm in short axis when assessed by CT scan or MRI (CT scan slice thickness recommended to be no greater than 5 mm). At baseline and in follow-up, only the short axis will be measured and followed.

Non-measurable disease: All other lesions (or sites of disease), including small lesions (longest diameter < 10 mm or pathological lymph nodes with ≥ 10 to < 15 mm short axis), are considered non-measurable disease. Bone lesions, leptomeningeal disease, ascites, pleural/pericardial effusions, lymphangitis cutis/pulmonitis, inflammatory breast disease, and abdominal masses (not followed by CT or MRI), are considered as non-measurable.

Note: Cystic lesions that meet the criteria for radiographically defined simple cysts should not be considered as malignant lesions (neither measurable nor non-measurable) since they are, by definition, simple cysts. Cystic lesions thought to represent cystic metastases can be considered as measurable lesions, if they meet the definition of measurability described above. However, if non-cystic lesions are present in the same patient, these are preferred for selection as target lesions.

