15.4 Methods for Evaluation of Measurable Disease

All measurements should be taken and recorded in metric notation using a ruler or calipers. All baseline evaluations should be performed as closely as possible to the beginning of treatment and

never more than 4 weeks before the beginning of the treatment.

The same method of assessment and the same technique should be used to characterize each identified and reported lesion at baseline and during follow-up. Imaging-based evaluation is preferred to evaluation by clinical examination unless the lesion(s) being followed cannot be imaged but are assessable by clinical exam.

Clinical lesions: Clinical lesions will only be considered measurable when they are superficial (e.g., skin nodules and palpable lymph nodes) and ≥ 10 mm diameter as assessed using calipers (e.g., skin nodules). In the case of skin lesions, documentation by color photography, including a ruler to estimate the size of the lesion, is recommended.

Chest x-ray: Lesions on chest x-ray are acceptable as measurable lesions when they are clearly defined and surrounded by aerated lung. However, CT is preferable.

Conventional CT and MRI: This guideline has defined measurability of lesions on CT scan based on the assumption that CT slice thickness is 5 mm or less. If CT scans have slice thickness greater than 5 mm, the minimum size for a measurable lesion should be twice the slice thickness. MRI is also acceptable in certain situations (e.g., for body scans).

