15.5 Response Criteria

15.5.1 Evaluation of Target Lesions

Complete Response (CR): Disappearance of all target lesions. Any pathological lymph nodes (whether target or non-target) must have reduction in short axis to <10 mm.

Partial Response (PR): At least a 30% decrease in the sum of the diameters of target lesions, taking as reference the baseline sum diameters.

Progressive Disease (PD): At least a 20% increase in the sum of the diameters of target lesions, taking as reference the smallest sum on study (this includes the baseline sum if that is the smallest on study). In addition to the relative increase of 20%, the sum must also demonstrate an absolute increase of at least 5 mm. (Note: the appearance of one or more new lesions is also considered progressions).

Stable Disease (SD): Neither sufficient shrinkage to qualify for PR nor sufficient increase to qualify for PD, taking as reference the smallest sum diameters while on study.

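### Inclusion criterion 9 accepts lymph nodes of 10 mm short axis on CT or MRI that Section 15.3 calls non-measurable, so a patient can be eligible with no valid target lesion

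*Combined protocol and SAP*

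**What the plan says.** - **Section 6.1, item 9 (entry).** Baseline measurable disease by RECIST v1.1 is required. The dimension is "longest diameter to be recorded for non-nodal lesions and short axis for nodal lesions". The threshold is at least "10 mm with spiral CT scan, MRI, or calipers by clinical exam", for nodes and other lesions alike. The item then directs the reader: "See Section 15.4 for the evaluation of measurable disease".
- **Section 15.3 (assessment).** It opens with nearly the same general 10 mm sentence and then adds a nodal rule: "a lymph node must be ≥ 15 mm in short axis when assessed by CT scan or MRI". Its list of non-measurable disease includes "pathological lymph nodes with ≥ 10 to < 15 mm short axis". Target lesions are drawn from measurable lesions only.
- **Section 15.4 (where item 9 points).** It gives no 15 mm nodal minimum. It accepts clinical lesions that are "superficial (e.g., skin nodules and palpable lymph nodes) and ≥ 10 mm diameter as assessed using calipers".
- **Section 15.5.1 (response).** For complete response (CR): "Any pathological lymph nodes (whether target or non-target) must have reduction in short axis to" less than 10 mm. Partial response (PR) needs a fall of at least 30% in the sum of target diameters.
- **Sections 15.2, 17.2 and 17.5.2 (who is counted).** 15.2 restricts objective-response evaluation to patients with measurable baseline disease. 17.2 counts every dosed patient. 17.5.2 counts all eligible patients, with a possible exception for the untreated.

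**The concern.** The entry rule and the assessment rule disagree on nodes of 10 to under 15 mm on CT or MRI. A site that builds its eligibility checklist from 6.1 and follows the cross-reference to 15.4 never meets the 15 mm minimum.

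For a patient whose only disease is such a node, each way of proceeding causes a problem for the primary endpoint:

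- **The node is treated as non-measurable.** There is no target lesion, so a PR is impossible. The patient is not evaluable for objective response under 15.2 but is still in the denominator under 17.2.
- **The node is used as a target.** The entry size lies close to the nodal CR threshold, so a shrinkage too small for a PR can qualify as a CR.

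The final decision turns on 4 or 5 responses among 32 patients, so one or two such cases can matter. The stage 1 rule needs only 1 response in 18, so a single spurious response there carries the trial forward.

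**Working it through.** **1. The plan's own design figures.** Section 17.1 uses a Simon two-stage design: 18 patients then 14 more, continuing with at least 1 response, with 5% against 20%. Early stopping at 5% is 0.95^18 = 0.397, matching the stated 40%. Section 5.2 calls the trial negative at 3 or fewer responses and 17.1 at 4 or fewer. The exact two-stage results are:

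| Positive if | Type I error at 5% | Power at 20% |
|---|---|---|
| ≥4 of 32 | 0.072 | 0.901 |
| ≥5 of 32 | 0.020 | 0.793 |

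The disagreement on the cut-off is a separate matter. Both cut-offs are carried below. The illustrations use a single-stage binomial with n = 32, which gives starting values of 0.074 and 0.907 (≥4) and 0.020 and 0.796 (≥5), close to the exact ones.

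**2. Node arithmetic.** Percentage fall = (baseline − follow-up) / baseline.

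| Short axis | Fall | Nodal CR threshold (<10 mm) met | 30% fall reached |
|---|---|---|---|
| 10 to 9 mm | 1/10 = 10% | yes | no |
| 11 to 9 mm | 2/11 = 18% | yes | no |
| 12 to 9 mm | 3/12 = 25% | yes | no |
| 14 to 9 mm | 5/14 = 36% | yes | yes |

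From 15 mm, getting below 10 mm takes a fall of more than 5/15 = 33%, which already exceeds the PR threshold. The anomaly therefore disappears under the minimum in 15.3.

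**3. Illustration: false responses at a true 5%.** The documents give neither the number of such patients (k) nor the chance that one reading falls below 10 mm through measurement variation (q). Assumptions: k = 1 to 3 of 32, and q = 0.20 to 0.50. An affected patient responds with probability 1 − (1 − 0.05)(1 − f), and the other 32 − k with probability 0.05. The primary endpoint needs confirmation at 4 weeks or later, so:

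- independent readings: f = q², that is 0.04 to 0.25, giving response probabilities of 0.088 to 0.2875;
- fully correlated readings: f = q, that is 0.20 to 0.50, giving 0.24 to 0.525.

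| | k = 0 | Independent: k=1, q=0.2 to k=3, q=0.5 | Fully correlated: k=1, q=0.2 to k=3, q=0.5 |
|---|---|---|---|
| P(≥4 responses) | 7.4% | 7.9% to 19.1% | 9.9% to 34.9% |
| P(≥5 responses) | 2.0% | 2.2% to 7.0% | 3.0% to 15.2% |

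**4. Illustration: lost power at a true 20%.** Worst case: k = 3 and none can respond, leaving 29 patients at 0.20. P(≥4) falls from 0.907 to 0.860, and P(≥5) from 0.796 to 0.716. With k = 1 the values are 0.893 and 0.771.

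**The case against.** The strongest reply is that item 9 is an incomplete summary, not a competing rule. It invokes RECIST v1.1, its sentence nearly repeats the opening of 15.3, and 15.3 then supplies the specific nodal minimum. Targets come only from measurable lesions, so an assessor working from Section 15 would not choose a 12 mm CT node. Section 15.8 adds independent review of all responses. This narrows the problem without removing it. Eligibility is decided from 6.1, whose cross-reference misses the 15 mm minimum. The independent review takes place at study completion, too late to undo an enrolment or inform the stage 1 decision.

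A reader might infer three stronger things that the documents do not support:

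- **That these patients cannot respond.** They cannot have a PR. But 15.5.2 sets CR for non-target nodes at under 10 mm, and 15.5.3 has a table for non-measurable disease in which non-target CR is an overall CR. The power loss above is therefore an upper bound. For the same reason, a small-change CR in a small node does not arise only from using it as a target.
- **That a 1 mm change will be counted as a CR.** This is the boundary case: a node of exactly 10 mm, no other persisting lesion, and confirmation at 4 weeks or later.
- **That the false-positive risk is 16-35%.** That range needs 3 such patients and treats q as the final false-response rate, which ignores confirmation unless repeat readings are fully correlated.

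The share of affected patients is unknown. The population has unresectable or metastatic disease, and skin lesions measured by calipers also count as measurable. Few patients may have small nodes alone.

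**Conclusion.** The inconsistency is real and is visible in the text without any calculation. A node of 10 to under 15 mm short axis on CT or MRI satisfies 6.1, item 9, and fails 15.3. A patient with nothing else is eligible and counted under 17.2, but has no valid target lesion.

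The size of the consequence cannot be established from the documents. Under the stated assumptions (1 to 3 of 32 patients, single-reading false rate 20-50%, true rate 5%), the chance of at least 4 responses goes from 7% to about 8-19% with independent confirmatory readings and to 35% at most. For at least 5 responses it goes from 2% to about 2-7%, and to 15% at most. The worst-case power at a true 20% is 0.86 instead of 0.91 (≥4) or 0.72 instead of 0.80 (≥5), with a smaller real loss because a non-target CR is possible. The point should be corrected. It does not show that the design's error rates fail.

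**What to change.** - In 6.1, item 9, state that a lymph node assessed by CT or MRI is measurable only at 15 mm short axis or more, and require at least one lesion that is measurable under 15.3.
- Change the cross-reference in item 9 to cite both 15.3 and 15.4.
- In the same edit, reconcile the 10 mm caliper wording for palpable nodes in 15.4 with 15.3, which states its 15 mm minimum for CT and MRI only. Changing item 9 alone, with a blanket 15 mm rule for all nodes, would create a new conflict with 15.4.
- Update the eligibility checklist to match.

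The cost is a few sentences and a checklist revision. A few patients whose only disease is small nodes become ineligible. The sample size does not change.

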6.2 Exclusion Criteria

1. At least 21 days must have elapsed since the last dose of systemic chemotherapy or immunotherapy and the first dose of study drug.
2. At least 14 days must have elapsed since the last dose of radiation therapy and the first dose of study drug.
3. Patients who have previously been treated with a JAK inhibitor.

4. Patients who are receiving any other investigational agents concurrently.
5. Patients who have had recent major surgery within a minimum 4 weeks prior to starting study treatment, with the exception of surgical placement for vascular access.
7. Patients with a history of allergic reactions attributed to compounds of similar chemical or biologic composition to ruxolitinib.
8. Patients with symptomatic or growing brain metastases. Patients with brain metastases that have been treated and have remained stable for at least one month prior to initiation of study therapy are eligible.
9. Concurrent use of strong CYP3A4 or CYP3A4 substrate drugs with a narrow therapeutic range within 14 days or 5 drug half-lives, whichever is longer, before start of study drug. A list of strong CYP3A4 and 2C8 inhibitors and inducers can be found in Appendix C.
10. HIV-positive patients on combination antiretroviral therapy are ineligible because of the potential for pharmacokinetic interactions with ruxolitinib. In addition, these patients are at increased risk of lethal infections when treated with marrow-suppressive therapy.
11. Subjects with known active hepatitis B or C, or chronic hepatitis B or C requiring treatment with antiviral therapy.
12. Uncontrolled intercurrent illness including, but not limited to, ongoing or active infection, symptomatic congestive heart failure, unstable angina pectoris, cardiac arrhythmia, or psychiatric illness/social situations that would limit compliance with study requirements.
13. Patients being actively treated for a second malignancy.

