5. STUDY DESIGN

5.1 General Design

This is an open-label, multi-center, Phase II study to evaluate the efficacy of ruxolitinib in post-transplant patients with advanced cutaneous squamous cell carcinoma.

Study Intervention: In a safety lead-in of 6 patients, subjects will receive ruxolitinib 15mg BID. After 4 weeks, if dose-limiting toxicities (DLT) are observed in 1 or fewer patients, the study will enter stage 1 of the Simon two-stage design where all subsequent patients will receive a starting dose of ruxolitinib 15mg BID. If more than 1 DLTs are observed, another cohort of 6 patients will be treated at a dose of 10mg BID. If less than 2 DLTs are observed at the new dose of 10mg, then the study will proceed to stage I using this dose; otherwise the study will stop.

Individual subjects may have dose reductions of ruxolitinib during the course of treatment, based upon safety laboratory assessments.

Schedule of Evaluations: Subjects will have regularly scheduled study visits at the clinical site on Day 1 and Day 15 (\pm 3 days) of the first cycle, then on Day 1 (\pm 3 days) of every subsequent cycle (starting cycle 2), where safety assessments, including laboratory assessments, vital signs, and physical examinations will be performed (see Section 12 for study calendar).

Response to treatment will be determined by CT scans of the chest, abdomen, and pelvis with contrast. The overall response rate for the primary endpoint evaluation will be determined by RECIST v1.1 criteria. In patients who are unable to get a CT scan w/ contrast due to renal function (or any other reason), an MRI with and without contrast may be used instead. Imaging will be performed at the following time points:

| | |
|--------------------------------------|---|
| Baseline scan | Baseline scan within 4 weeks prior to first treatment |
| Weeks 1 – 32 | Every 8 weeks +/- 1 week (at weeks 8, 16, 24, 32) |
| Weeks 33 – until disease progression | Every 12 weeks +/- 1 week (at weeks 44, 56, 68, 80, 92, 104) |
| 2 years | If subjects achieve ongoing disease control at 2 years, patients will be continued on study treatment and observed with imaging every 12 weeks +/- 2 weeks. |

Duration of treatment: Subjects will continue treatment until confirmed radiographic disease progression, intolerable toxicity or side effects (Section 6.5.1).

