12.2.3 Schedule of Disease monitoring

A CT scan of the chest, abdomen, and pelvis with contrast will be obtained to evaluate disease status. A scan will be obtained at baseline (within 28 days of first study drug dose), then every 8 weeks for the first 32 weeks. After week 32, a CT chest, abdomen, pelvis with contrast will be performed every 12 weeks until disease progression, withdrawal from study, or ongoing disease control at 2 years (defined as at least stable disease at this point). For patients who achieve ongoing disease control at 2 years, subjects will be observed with a CT chest, abdomen, pelvis with contrast every 12 weeks. In patients who are unable to get a CT scan with contrast due to renal function (or any other reason), an MRI with and without contrast may be used instead. If the patient develops disease progression during this observation time, they will have the option of restarting study treatment at that time.

Table 7: Schedule of Disease Monitoring.

| | |
|--------------------------------------|---|
| Baseline scan | Baseline scan within 4 weeks prior to first treatment |
| Weeks 1 – 32 | Every 8 weeks +/- 1 week (at weeks 8, 16, 24, 32) |
| Weeks 33 – until disease progression | Every 12 weeks +/- 1 week (at weeks 44, 56, 68, 80, 92, 104) |
| 2 years | If subjects achieve ongoing disease control at 2 years, patients will be continued on study treatment and observed with imaging every 12 weeks +/- 2 weeks. |

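### The baseline scan may predate the end of prior radiation or systemic therapy, and the conditions for irradiated target lesions are left undefined, so earlier shrinkage can count toward the response endpoint

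*Combined protocol and SAP*

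**What the plan says.** **Prior therapy.** Section 6.2 gives two minimum intervals before the first dose. For radiation: "At least 14 days must have elapsed since the last dose of radiation therapy and the first dose of study drug". For systemic treatment: "At least 21 days must have elapsed since the last dose of systemic chemotherapy or immunotherapy and the first dose of study drug". Section 6.1 expects pretreated patients ("A maximum of 4 prior therapies for metastatic disease are allowed") and has no criterion requiring progression on or after the last of those treatments.

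**Baseline imaging.** Section 5.1 and Table 7 in Section 12.2.3 both ask for a "Baseline scan within 4 weeks prior to first treatment". Section 15.4 asks for baseline evaluations close to the start of treatment and "never more than 4 weeks before the beginning of the treatment". The opening paragraph of Section 13 puts baseline evaluations within 1 week of starting therapy but allows 4 weeks for scans and x-rays. None of these places ties the scan to the end of prior therapy.

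**Irradiated lesions.** Section 15.3 says "Tumor lesions that are situated in a previously irradiated area might or might not be considered measurable". It adds that if the investigator wishes to include them, the protocol must define the conditions. Sections 6 and 15 contain none.

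**Endpoint.** Partial response in Section 15.5.1 is a fall of at least 30% in the sum of target diameters, "taking as reference the baseline sum diameters". The primary endpoint (Section 17.2) is best response within 24 weeks, confirmed at least 4 weeks later.

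**The concern.** The scan window is longer than both washouts. A patient can be scanned, finish radiation or receive a last systemic dose, wait out the required interval and start ruxolitinib, all within the rules. The week 8 scan is then compared with a measurement made before the earlier treatment ended, and any shrinkage from that treatment is read as response to ruxolitinib.

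There is no control arm in which the same carry-over would appear. The comparison is with a fixed 5% rate, and Stage 1 is passed by a single response in 18 patients, so a few misattributed responses could change the decision.

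**Working it through.** **1. Dates (day 0 = first ruxolitinib dose).**
- Earliest compliant baseline scan: day −28.
- Latest compliant last radiation dose: day −14. The scan can precede it by 28 − 14 = 14 days.
- Latest compliant last chemotherapy or immunotherapy dose: day −21. The scan can precede it by 28 − 21 = 7 days.

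**2. The plan's own design figures.** Inputs from Section 17.1: null rate 5%, target rate 20%, 18 patients in Stage 1, stop if there are no responses, 32 in total. The final rule differs by section: Section 5.2 calls the trial negative at 3 or fewer responses, while the synopsis and Section 17.1 say 4 or fewer. Both are carried below.

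P(stop at Stage 1) = (1 − p)^18. At p = 0.05 this is 0.95^18 = 0.397, matching the stated 40%.

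P(positive) = Σ over x = 1 to 18 of P(X₁ = x) · P(X₂ ≥ r + 1 − x), where X₁ ~ Bin(18, p), X₂ ~ Bin(14, p) and r is the largest negative count.

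| Final rule | p = 0.05 | p = 0.20 |
|---|---|---|
| positive at ≥4/32 (r = 3) | 0.072 | 0.901 |
| positive at ≥5/32 (r = 4) | 0.020 | 0.793 |

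The stated 90% power is met only with the first rule. That conflict is a separate matter.

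**3. Sensitivity to carry-over.** Let q be the share of patients without a drug response who are nevertheless scored as confirmed responders because of prior therapy. The documents give no value for q; it is an assumption. With a true drug rate of 5%, the apparent rate is p* = 1 − 0.95(1 − q) = 0.05 + 0.95q. Putting p* into the formulas above:

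| q | p* | false positive, ≥4/32 | false positive, ≥5/32 | passes Stage 1 |
|---|---|---|---|---|
| 0 | 0.0500 | 7.2% | 2.0% | 60% |
| 1% | 0.0595 | 11.8% | 3.9% | 67% |
| 2% | 0.0690 | 17.3% | 6.6% | 72% |
| 3% | 0.0785 | 23.6% | 10.1% | 77% |
| 5% | 0.0975 | 37.4% | 19.6% | 84% |

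The planned 10% is exceeded at q = 1% under the first rule and at q = 3% under the second.

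**4. A lower range, using a figure in the protocol.** The synopsis gives a chemotherapy response rate of 5–10% in transplant recipients. Suppose, again as an assumption, that 5–20% of patients have prior therapy overlapping the scan window and that 5–10% of those shrink enough to qualify.
- Low end: q = 0.05 × 0.05 = 0.0025, so p* = 0.0524.
- High end: q = 0.20 × 0.10 = 0.02, so p* = 0.0690.
- False-positive rate: 8–17% with ≥4/32, 2–7% with ≥5/32.
- Chance of passing Stage 1: 62–72%.

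**The case against.** **The window is narrow.** For systemic therapy the overlap is at most 7 days. For radiation, the patient must be scanned and then irradiated within the period before the first dose. Nothing in the documents shows how often this would happen. This stands, and it is why the size is only illustrative.

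**Scoring a response is demanding.** Up to five target lesions, representative of all involved organs, must shrink by 30% in sum, with no new lesions or non-target progression, and the response must be confirmed. Radiation to one site may not achieve that in multi-site disease. This lowers q but does not make it zero. Shrinkage from earlier treatment can persist to the confirmatory scan, and the independent review in Section 15.8 would work from the same baseline.

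**An old scan can also work against response.** Growth between the scan and day 0 goes unrecorded and makes a 30% fall harder to reach. This is right: only the carry-over component is one-directional, and the net effect of an old scan is not.

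**Caliper measurements may already be covered.** Read plainly, the one-week rule in Section 13 places them after both washouts. The remaining problem is that Section 15.4 allows 4 weeks for all baseline evaluations, so the two sections need aligning.

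**Section 15.3 is not a permission.** A reader might infer that irradiated lesions may freely serve as targets. The text does not say so. It makes inclusion depend on conditions that the protocol must state; strictly read, without those conditions no such lesion is authorised. The defect is an unfinished clause that leaves the investigator without a criterion.

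**Conclusion.** The date gap is certain. The 28-day scan limit and the 14- and 21-day washouts are as written, and no section orders the scan after prior therapy or asks for progression since it. The missing conditions for irradiated lesions are equally plain.

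The effect on the trial's error rates is not established. It rests on an assumed q, and on each carry-over case being scored as a full confirmed response. Under the ≥4/32 rule q = 1% is enough to exceed the planned 10%; under the ≥5/32 rule it takes q = 3%. With the protocol's own chemotherapy response rate and an assumed 5–20% of patients affected, the ≥5/32 rule stays below 10% throughout.

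A reader might go further and infer that the false-positive rate is several times the planned level; q = 10%, for example, would give 69% or 50% under the two rules. No figure in the documents supports a q of that size. Nor does the point imply that the washouts themselves are wrong; their length is not judged here. This is a cheap improvement to the measurement rules.

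**What to change.** - **Sections 5.1, 12.2.3 (Table 7), 13 and 15.4:** require the baseline tumor scan to be taken after the last dose of any prior systemic therapy or radiation, still within 4 weeks of the first ruxolitinib dose. The washouts stay as they are and already leave at least 14 days (radiation) or 21 days (systemic therapy) for the scan.
- **Sections 13 and 15.4:** give one time limit for baseline caliper measurements.
- **Section 15.3:** complete the clause, so that a lesion in a previously irradiated field may be a target only if growth was documented after radiation ended. This also limits delayed radiation shrinkage, which scan timing alone would miss.
- **Patients already enrolled:** flag any baseline scan that predates the end of prior therapy and any irradiated target lesion, and report the response rate with and without those patients as a sensitivity analysis.

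The cost is an occasional repeat baseline scan. A few patients whose only measurable lesion is irradiated and not growing would no longer qualify.
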